#### **10.2**

#### **Sample Size and Accrual**

A total of 35 patients (as needed) with metastatic breast cancer which is HER2 negative will be enrolled into this study and receive durvalumab in combination with tremelimumab, in order to get 28 evaluable for response. 15 patients with ER-positive disease and 15 patients with ER-negative disease will be enrolled (i.e. 2 cohorts with 14 evaluable each). Patients who have completed the week 8 CT or nuclear bone scan will be evaluable for response endpoints. Bone scans will be done only if the patient has bone disease. PET-CT is acceptable in place of bone scan, if a bone scan is contra-indicated for a patient's disease. The same modality used at baseline should be used throughout.

Using a Simon's two-stage design, we assume the undesirable overall response rate (null hypothesis) to be approximately 10%, and the alternate hypothesis to be approximately 30% based on previously published and presented data. Eleven patients will be added in the first stage. If 2 or more respond, then an additional 16 patients will be added for a total of 27. If 6 or more respond, then the hypothesis that the response rate is at least 30% is supported. This design has a Type I error rate of 4% and 80% power, and has a 70% chance of stopping early for futility after the first stage if the true response rate is 10%. The design is based on the complete sample and is not stratified by estrogen receptor status. ORR will also be calculated separately by receptor status, but the study is not powered for analyses within these subgroups.

For the expansion cohort we expect the ORR based on RECIST v1.1 to exceed 30% given our preliminary data. Using a Bayesian design assuming a prior beta distribution with parameters 0.3 and 0.7, there is a posterior probability of 0.81 that the ORR exceeds 30% if 8 or more responses out of 20 evaluable patients are observed.

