#### **10.3**

#### **Data Analyses Plans**

The primary analysis will be on the intent-to-treat (ITT) population, including all evaluable patients. Best ORR defined as will be defined as number (%) of patients with at least one visit response of complete or partial response by the Response Evaluation Criteria in Solid Tumors (RECIST 1.1). Best objective response prior to disease progression will be used. The overall response rate will be estimated by the proportion of overall response, and its 80% confidence interval (CI) and 95% CI will be estimated using the exact binomial distribution.

Additionally, we will evaluate clinical benefit rate, defined as stable disease for  $\geq 12$  weeks complete or partial response using RECIST 1.1 guidelines in a similar manner. We will also perform similar analyses using Immune Related RECIST (irRECIST).

PFS is defined as the time from date of treatment initiation until date of documented disease progression or death (by any cause in the absence of progression). OS is defined as the time from the date of start of treatment until death due to any cause. For patients alive at the time of data cut-off, PFS and OS will be censored as of the last tumor assessment date or known to be alive, respectively. The PFS and OS will be estimated using the Kaplan-Meier method. The number, frequency, and severity of adverse events (as defined by the NCI Common Terminology Criteria for Adverse Events or CTCAE version 4.03) will be recorded.

Baseline percent PDL1 expression, TILs (sTILs, iTILs, and their ratio), and changes in T cell subpopulations will be used as a continuous variable to predict clinical benefit or overall response rates using appropriate statistical summaries. Cox proportional hazards regression will be used to compare how these biomarkers are associated with PFS and OS as well.

Changes from baseline in these biomarkers will also be analyzed to assess for pharmacodynamic effects of treatment. Continuous variables will be analyzed using either paired t-tests, signed rank tests or repeated measures analysis of variance.

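### Six responses in 27 would show that the ORR exceeds 10%, not that it is at least 30%; the reported analysis should also acknowledge the two-stage design

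*Combined protocol and SAP*

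**What the plan says.** Section 10.2 (Sample Size and Accrual) takes an ORR of about 10% as the null and about 30% as the alternative. Stage 1 has 11 patients; with at least 2 responders, stage 2 brings in 16 more, making 27. The success criterion at the end of stage 2 is worded: "If 6 or more respond, then the hypothesis that the response rate is at least 30% is supported". The operating characteristics are given separately as a type I error of 4%, power of 80%, and a 70% probability of a stage 1 stop at a true rate of 10%.

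Section 10.3 (Data Analyses Plans) estimates the ORR by the observed proportion, and "its 80% confidence interval (CI) and 95% CI will be estimated using the exact binomial distribution". No section gives a two-stage estimate, interval or p-value, or says how the 80% and 95% intervals relate to the six-response rule.

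Section 3.0 (Patient Eligibility) gives a different rule: 18 patients first, continue to 28 if 4 or more respond, with no final cut-off.

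**The concern.** The success statement names the wrong hypothesis. Crossing the boundary rejects 10%. The 30% rate is only the value at which power was calculated, so a result at the boundary is no evidence that the ORR reaches it. If the sentence is carried into a report, a response rate well below 30% could be presented as support for 30% or more. That overstates what a single-arm trial of this size can show.

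The second issue concerns reporting only. The data arise from a design that can stop at 11, while the planned estimate and intervals treat the final number as fixed. At the boundary, a fixed-sample calculation misses the design's own 4% level although the rule declares success.

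**Working it through.** **Inputs (Section 10.2).** Stage 1 has 11 patients; continue with 2 or more responses. Stage 2 adds 16, for a total of 27; success is 6 or more. Null 10%, alternative 30%. Sidedness is not stated, but only high counts lead to success, so the test is one-sided.

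**1. Reproduce the stated design.**

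P(success | p) = Σ over x = 2 to 11 of Bin(x; 11, p) × P[Bin(16, p) ≥ 6 − x]

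At p = 0.10:

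- x = 2: 0.21308 × 0.06841 = 0.01458
- x = 3: 0.07103 × 0.21075 = 0.01497
- x = 4: 0.01578 × 0.48527 = 0.00766
- x = 5: 0.00246 × 0.81470 = 0.00200
- x ≥ 6: 0.00030

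The sum is 0.0395 (stated 4%). At p = 0.30 the same formula gives 0.806 (stated 80%). Early stopping at 10% is P[Bin(11, 0.10) ≤ 1] = 0.697 (stated 70%). The design reproduces.

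**2. How often would the 30% statement be made?** The same formula gives:

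| True ORR | P(success) |
|---|---|
| 10% | 4.0% |
| 15% | 18.0% |
| 20% | 40.7% |
| 30% | 80.6% |

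**3. What the boundary result shows.** 6/27 = 22.2%. The planned exact intervals are 8.6% to 42.3% (95%) and 12.1% to 35.8% (80%). Both contain 30%, so 30% is not refuted, but both also contain rates far below it. Counts of 6, 7 and 8 (22.2%, 25.9%, 29.6%) would all trigger the statement with an observed rate under 30%.

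**4. Effect of the two stages on reporting.**

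- One-sided p against 10% at 6/27: 0.0395 from step 1, against P[Bin(27, 0.10) ≥ 6] = 0.0471 as a fixed sample.
- Matching level: 4% in each tail is 100% − 2 × 4% = 92% two-sided. Ranking every stage 1 stop below every stage 2 result and solving for 4% in each tail gives 10.03% to 42.3% at 6/27. The lower limit just clears 10% because 0.0395 is below 0.04. The fixed-sample 92% interval starts at 9.6%. (The two-stage 92% upper limit equals the planned 95% one only by coincidence of rounding.)
- Bias of the raw proportion, over all outcomes: −2.1 points at a true ORR of 10%, −2.6 at 15%, −2.5 at 20%, −1.5 at 30%.
- Unbiased two-stage estimate at 6/27: Σ C(10, x−1)·C(16, 6−x) ÷ Σ C(11, x)·C(16, 6−x), x = 2 to 6, = 61,412 ÷ 239,954 = 25.6%.

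**5. Dependence on which rule was run.** Under Section 3.0 (18 then 28), with an assumed final cut-off of 6, type I error is 0.039, power 0.805 and early stopping at 10% is 0.90. The stated 70% therefore fits only the Section 10.2 rule. Section 1.7.3 reports 3 responses in the first 18 evaluable patients. Under Section 3.0 that would be a stage 1 stop, where the planned interval would need no adjustment under this ordering.

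**The case against.** The best defence is that the count rule is the decision criterion, its error rates are as stated, and the intervals are for estimation only. Describing a rejected null as support for the alternative is also common shorthand in two-stage designs. All of that stands for the decision. It does not rescue the sentence, which asserts a rate of at least 30% when only 10% has been tested.

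A reader might infer three stronger criticisms of the intervals. None is supported.

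- *The stopping rule is why the 95% interval contains 10% at 6/27.* The two-stage 95% interval, 9.0% to 44.7%, contains it too. The cause is the level: 2.5% in each tail against about 4% one-sided.
- *The planned intervals under-cover.* Under the Section 10.2 design the 95% interval covers 98.7% at a true ORR of 10% and 96.0% at 30%; the 80% interval covers about 96% and 87.3%. The lowest values on a fine grid are 94.9% and 79.4%, which is essentially nominal.
- *Success cannot be reconciled with any planned interval.* The planned 80% interval starts at 12.1% at 6/27 and 9.3% at 5/27, so it agrees with the rule on both sides. A plain exact 90% interval also excludes 10% at 6/27 (from 10.1%).

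Replacing the planned analysis would not be a clear gain. The two-stage 80% interval at 5/27 starts at 10.2%, excluding 10% where the rule says fail. Given that stage 2 is reached, the unbiased estimator is off by +11.5 points at a true ORR of 10%, against +4.7 for the raw proportion. The overall bias of the raw proportion is downward, so it does not exaggerate efficacy.

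**Conclusion.** The concern holds for the stated conclusion: six or more responses in 27 support an ORR above 10% and no more. As written, the 30% claim would be made 18% of the time at a true ORR of 15% and 41% at 20%. The missing two-stage reporting is secondary. At the boundary it moves the p-value from 0.047 to 0.0395 and the 95% limits by 0.4 points (lower) and 2.4 points (upper). It changes neither the decision nor the design's error rates.

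These figures assume that the 11-then-27 rule was the one applied, with exactly 27 evaluable patients. Section 10.2 also targets 28 evaluable, and Section 3.0 conflicts with it. The documents do not show the final evaluable number for the general cohort.

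**What to change.** 1. Reconcile the two-stage rules in Sections 3.0 and 10.2, and state which was run and on how many evaluable patients. The adjustment depends on this.
2. In Section 10.2, replace the success conclusion with: if six or more of 27 respond, the null of 10% is rejected and the ORR is concluded to exceed 10%.
3. In Section 10.3, keep the proportion and the 80% and 95% exact intervals. For the general cohort add the two-stage one-sided p-value, or the stagewise exact interval at the level matching the 4% test (about 92% two-sided). The unbiased estimate may be shown as an option.
4. State that the response count, not the 80% or 95% interval, decides success.
5. Leave the simple exact interval for the expansion cohort, for which Section 10.2 gives no interim stopping rule.

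The cost is a few sentences and a few lines of code. Appendix E records that general-cohort enrolment is complete, so only reporting changes; no new patients or data are needed.

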### **2.2 Secondary Objectives & Endpoints**

2.2.1 To evaluate PFS and OS in patients with metastatic HER2 negative breast cancer treated with durvalumab in combination with tremelimumab.

Secondary endpoints include PFS and OS, where PFS is defined as the time from date of treatment initiation to date of documented disease progression or death (by any cause in the absence of progression), and OS is defined as the time from date of treatment initiation until death due to any cause.

2.2.2 To evaluate safety and tolerability.

The endpoints will be the number, frequency, and severity of adverse events (as defined by the NCI Common Terminology Criteria for Adverse Events or CTCAE version 4.03) will be recorded.

2.2.3 To evaluate clinical benefit rate in this population.

Clinical benefit rate is defined as stable disease (SD) for  $\geq$  12 weeks + PR + CR.

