**4.1.1 Continuation of Investigational Therapy after Radiographic Progression (Pseudoprogression)**

Treatment may be continued in the setting of pseudoprogression (radiographic increase or new lesions felt to be due to inflammation/immune response) as long as all of the following criteria are met:

- Absence of clinical symptoms or signs indicating clinically significant PD.
- No significant decline in Eastern Cooperative Oncology Group (ECOG) performance status (PS >2 or as deemed by treating investigator).
- Absence of rapid PD or threat to vital organs/critical anatomical sites (e.g., spinal cord compression) requiring urgent alternative medical intervention
- Patients are made aware of the potential benefits and risks of continuing study therapy in the setting of Pseudo-Progression. Patients continuing therapy in the setting of suspected pseudoprogression should continue with treatment according to whether they in the induction phase (durvalumab 1500mg intravenously (IV) every 4 weeks for a total of 4 doses, and tremelimumab 75mg IV every 4 weeks for a total of 4 doses) or maintenance phase (durvalumab 750mg every 2 weeks). For example, a patient with suspected pseudoprogression after cycle 2 of durvalumab and tremelimumab would continue onto cycle 3 of durvalumab and tremelimumab rather than durvalumab single agent portion of the regimen (maintenance phase).

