## 5.0 STUDY PROCEDURES

Visit Number	1	2	3	4	5	6	7	8	9	10	11	x	x + 1	x + 2	x + 3	x + 4
Procedure/Study Day	SV 	D1	D14 (±3D)	W4 (±3D)	W8 (±3D)	W12 (±3D)	W16 (±3D)	W18 (±3D)	W20 ** (±3D)	W22 (±3D)	W24 (±3D)	Off Treatm ent 	3M (±1 month)	6M ±1 month)	9M (±1 month)	12M + q6M (±1 month)
Informed consent	X															
Durvalumab 1500mg		X		X	X											
Durvalumab 750mg							X	X	X	X	X					
Tremelimumab 75mg		X		X	X	X										
CT chest, abdomen, pelvis; nuclear bone scan 	X				X		X				X	X				
Assessment of AEs/SAEs 		X	X	X	X	X	X	X	X	X	X	X	X			
Concomitant medications (including next line therapy after off treatment, response)	X	X	X	X	X	X	X	X	X	X	X	X	X			
Physical examination  , weight	X		X	X	X	X	X		X		X	X	X	X	X	
Height (prior to dosing)	X															
ECOG performance status	X			X	X	X	X		X		X	X	X	X	X	
12-lead Electrocardiogram 	X															
Vital signs 	X	X	X	X	X	X	X	X	X	X	X	X				
Urinalysis 	X															
Hepatitis serologies 	X															
HIV antibody	X															
Pregnancy test 	X															
Serum chemistry 	X	X	X	X	X	X	X	X	X	X	X	X	X			
lactate dehydrogenase, GGT, lipase, uric acid and amylase 	X	X	X	X	X	X					X	X				
Hematology 	X	X	X	X	X	X	X	X	X	X	X	X	X			
Coagulation parameters 	X			X	X							X				
Thyroid function tests 	X	X		X	X	X					X	X				
Research blood samples 	X				X							X 				
Tumor biopsy 	X				X						X					

**\*\* Visits 8 through 11 will repeat for a total of up to 18 doses of durvalumab, or until progressive disease (see 4.1.1) or unacceptable toxicity, with CTs and bone scan done every 8 weeks.** Scans are to be completed every 8 weeks, regardless of drug holds or treatment delays. (Note: Bone scans will be done only if the patient has bone disease. PET-CT is acceptable in place of bone scan, if a bone scan is contra-indicated for a patient's disease. The same modality used at baseline should be used throughout). Patients may continue on therapy after progression or after initial 52 week treatment period as specified in Sections 4.1.1 and 4.1.2. Abbreviations: SV (screening visit)

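### The PFS censoring sentence in Section 10.3 omits the condition that the patient is progression-free, so read literally it censors progressed patients who are still alive

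*Combined protocol and SAP*

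**What the plan says.** Section 10.3 first defines the endpoint: "PFS is defined as the time from date of treatment initiation until date of documented disease progression or death", where death counts from any cause if there was no progression before it. Section 2.2.1 says the same ("PFS is defined as the time from date of treatment initiation to date of documented disease progression or death"), and Sections 6.3 and 10.1 repeat it. Under all four statements a patient with documented progression has a PFS event on that date, whether or not the patient is later alive.

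Two sentences after the definition, Section 10.3 gives the censoring rule: "For patients alive at the time of data cut-off, PFS and OS will be censored as of the last tumor assessment date". The few words that close the sentence give OS a different date, the one on which the patient was last known to be living, so that the tumor assessment date belongs to PFS. They do not restrict which patients are censored. The estimator follows: "The PFS and OS will be estimated using the Kaplan-Meier method". The same section plans Cox regression of biomarkers on PFS and OS. No other section contains a PFS censoring rule.

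**The concern.** The two endpoints share a lead-in condition that suits only one of them. For OS, alive at cut-off and event-free are the same state. For PFS they differ: a patient who progressed at the week 8 scan and is alive at cut-off has had the event, yet meets the stated condition for censoring.

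The trial's design lets this situation arise. Sections 4.1 and 4.7 plan three years of follow-up for survival and progression, so a progressed patient can be alive when data are cut. If the sentence were programmed as written, true progression events would drop out of the PFS estimate and out of the event indicator in the PFS Cox models. With a single arm, PFS is read as an absolute value, and no comparator shares the error.

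**Working it through.** The documents state no median PFS, event count or PFS power, so there is no figure of the plan's own to reproduce. The check has three parts.

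**1. Direction.** Compare the two readings patient by patient.

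| Status at cut-off | By the definition | By the literal sentence |
|---|---|---|
| Dead | Event at progression or death | The same |
| Alive, not progressed | Censored at last assessment | The same |
| Alive, progressed | Event at progression | Censored at last assessment |

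Only the third row changes. If progression is documented at a tumor assessment, the last assessment falls on or after the progression date. It can fall well after it, because Section 4.1.1 says "Treatment may be continued in the setting of pseudoprogression" and Section 5.0 says "Scans are to be completed every 8 weeks, regardless of drug holds or treatment delays". At every event time the literal reading therefore has no more events and no fewer patients at risk. Each Kaplan-Meier factor, 1 − d/r, is equal or larger, so the curve is equal or higher. In 8,000 simulated trials the literal curve was never below the definition-based curve at 3, 6 or 12 months.

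**2. Illustration from the interim table.** Section 1.7.3 lists 11 of 18 evaluable patients as PD. It gives no progression dates and no survival status. Suppose all 11 progressed at month 2 and the other 7 remained event-free. PFS just after month 2 is 7/18 = 0.39 by the definition. If k of the 11 are alive at cut-off and are censored at month 2, the literal sentence gives 1 − (11 − k)/18:

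- k = 3: 10/18 = 0.56
- k = 6: 13/18 = 0.72
- k = 9: 16/18 = 0.89

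**3. Size under a model.** None of these assumptions is in the documents: exponential time to progression (median 2 or 4 months), plus independent exponential survival after progression (median 10 or 16 months with the former, 8 or 14 with the latter). Overall survival then has a median of about 13 to 20 months. Let λ = ln 2 / median time to progression and μ = ln 2 / median post-progression survival. If progressed patients who are alive are censored at the progression scan, the cumulative hazard that Kaplan-Meier estimates in large samples is

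H(t) = λt − (λ/μ) · A · (e^(μt) − 1),

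and the literal median solves H(t) = ln 2 = 0.693. With every patient cut off at 36 months, A = e^(−36μ). With cut-offs uniform over 6 to 36 months, A = (e^(−6μ) − e^(−36μ))/(30μ), valid for t up to 6.

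Worked case, medians 2 and 10: λ = 0.3466, μ = 0.0693, λ/μ = 5.

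- Cut-off 6 to 36 months: A = (0.6598 − 0.0825)/2.079 = 0.2776. At t = 2.9, H = 1.005 − 5 × 0.2776 × 0.2226 = 0.696, so the median is about 2.9.
- All at 36 months: A = 0.0825. At t = 2.2, H = 0.7625 − 5 × 0.0825 × 0.1647 = 0.695, so the median is about 2.2.

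All four settings, in months (the 7.5 lies beyond month 6 and comes from simulation of the same model):

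| True median PFS | Median post-progression survival | Cut-off 6–36 months | All followed 36 months |
|---|---|---|---|
| 2 | 10 | 2.9 | 2.2 |
| 2 | 16 | 3.8 | 2.6 |
| 4 | 8 | 5.5 | 4.2 |
| 4 | 14 | 7.5 | 4.9 |

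In the 6–36 month column, 29% to 48% of patients have progressed and are alive. If scans continued to cut-off in all of them, the opposite extreme, that column would rise to about 3.7 and 6.7 months with the shorter survival, and to above 9 and about 16 with the longer.

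A separate simulation at the expansion cohort's planned size shows the same dependence on cut-off. It takes n = 20 and two patients per month from Section 3.0, with 8-weekly scans. It assumes median time to progression of 4 months, post-progression survival of 6 or 12 months, and a last scan 0 or 3.68 months after progression. By the definition, 6-month PFS is about 0.35. By the literal sentence it depends on the cut-off after last enrolment:

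- 3 months: 0.64–0.78
- 6 months: 0.56–0.72
- 12 months: 0.45–0.61 (expected events fall from about 19 to 10–14 of 20)
- 36 months: 0.35–0.41

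**The case against.** The strongest reply is that the definition already settles the matter. It stands two sentences earlier, is repeated in three other sections, and gives every progressed patient an event date. Censoring by convention applies to patients whose event has not been observed, and the evident purpose of the sentence is to fix censoring dates. A careful analyst would read it as alive and event-free. That largely stands: the documents do not show a deliberate choice to censor progressed patients, and a reader who infers one goes too far. What remains is that the plan's only PFS censoring rule gives the wrong condition, and the correct result depends on the analyst overriding it.

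A reader might also infer that median PFS would be nearly doubled, from 2 to 3.8 or from 4 to 7.5. The documents do not support this as an expectation. Those values need a mix of short follow-up and the longer assumed survival. With 36 months of follow-up for every patient, in line with the planned three years, the same model gives much less. The 36-month case does assume that survival is still tracked after progression. Section 4.8 ends observation when another anticancer therapy starts, while Sections 4.1 and 4.7 plan continued follow-up.

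Nor do the documents show that many progressed patients will be alive at cut-off. The interim table reports response categories only.

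Finally, PFS is secondary and descriptive, with no threshold or comparator. The ORR analysis, the Simon rule and the Bayesian criterion for the expansion cohort do not use it. This stands in full.

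**Conclusion.** The sentence is wrong as written for PFS and right for OS. It is best treated as a drafting omission of the progression-free condition. If followed, the direction of error is known, given that progression is documented at an assessment: PFS is overstated or unchanged, never understated. The consequence is confined to the secondary PFS estimate and the exploratory Cox models.

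The size cannot be stated for this trial. It is driven by how many progressed patients are alive at cut-off and how long scans continue after progression. Under the exponential model above, with censoring at the progression scan, the literal rule turns a true median of 2 months into about 2.2 to 2.6 with 36 months of follow-up for all, and 2.9 to 3.8 with cut-offs over 6 to 36 months. For a true median of 4 months the figures are about 4.2 to 5 and 5.5 to 7.5. Mature follow-up makes the error small; an early cut-off makes it large.

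**What to change.** Replace the censoring sentence in Section 10.3 with: *Patients alive without documented progression at data cut-off are censored for PFS at the last tumor assessment; patients alive at data cut-off are censored for OS at the date last known alive.*

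This agrees with the definition in all four sections and leaves OS unchanged. It costs one sentence and alters no procedure, data collection or sample size. The Amendment 12 summary of changes records that the study closed in July 2020 for low accrual. If the plan will not be amended again, the analysis report should state that documented progression was counted as a PFS event regardless of vital status at cut-off, in both the Kaplan-Meier and the Cox analyses.

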### **2.3 Exploratory Objectives & Endpoints**

2.3.1 To evaluate if serum and tissue-based biomarkers including: circulating tumor DNA, immunohistochemical expression of PD-L1; tumor infiltrating lymphocytes (TILs); changes in tissue and peripheral T cell receptor genotype; mutational and neoantigen burden; and immune-related candidate gene expression signatures predict response to durvalumab in combination with tremelimumab.

2.3.2. To determine the response rate (RR) and duration of response(DoR) of subsequent next line therapy after progression on durvalumab/ tremelimumab study regimen, for those patients who are able to submit detailed follow up data about subsequent treatment and response.

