## **9.0 CORRELATIVES/SPECIAL STUDIES**

**Please refer to laboratory manual for additional details**

### **9.1 Tissue sample collection guidelines**

A fresh tissue biopsy of the primary tumor or a metastatic site at baseline and after 2 cycles of treatment will be collected. Re-biopsy after cycle 2 must be of the original biopsy site. In case of complete response, a biopsy of the original site will be re-biopsied, if feasible (i.e. chest wall metastasis), or another metastatic site may be used. The tumor lesion planned for biopsy must not be used as index lesion for assessment of disease unless there are no other lesions suitable for biopsy or the lesion used for biopsy is  $\geq 2$  cm in its longest diameter.

Fresh tissue biopsies will be performed using an image-guided core needle at the aforementioned time points (pretreatment, after 2 cycles) according to institutional practice. If clinically practical, subjects will undergo 4 core biopsies at each scheduled biopsy time point, ideally at least 3 core biopsies. Skin punch biopsies are acceptable, however, at least 2 punch biopsies that are at least 8mm in shortest diameter are necessary. All tissue samples will be immediately frozen in liquid nitrogen and then stored at  $-80^{\circ}\text{C}$ , full details are provided in the lab manual. Collected tissues at baseline will undergo a touch prep to be sent to pathology for standard of care testing.

Tumor samples will be stored and may be used for additional correlative studies at a later date such as, but not limited to, immunohistochemistry, tumor mutation analysis and proteomic analysis.

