#### **9.2 Blood sample Collection Guidelines**

Research blood samples will be collected at baseline and 2 months, and at end of study or time of discontinuation).

80 mL of whole blood should be collected per lab manual instructions. Please ensure that tubes are completely filled at time of collection.

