For analysis of each T cell receptor clonotype, we will apply a newly-developed algorithm Bowtie2 aligner (Ref; Nature methods 2012; 9:357-9), in collaboration with Profs. [name] and [name] in Human Genome Center, The University of Tokyo. We will assign each of V, (D), J and C segments in the TCRA and TCRB reference sequences provided by IMGT/GENE-DB (Ref; Nucleic acids research 2005; 33:D256-61). By our approach, we will also identify novel exons that are not deposited in the reference sequence database. After decomposition of T cell receptor sequencing reads into V, (D), J and C segments, we will determine amino acid sequences of CDR3 (complementarity determining region 3), which plays a critical role in recognition of antigen. We will also calculate the diversity index (inverse Simpson's index) in CDR3 sequences to assess overall diversity and clonality in the T cell receptor clonotypes. Descriptive statistics will be used to assess differences from baseline to two months, and their relationship with clinical endpoints.

Determination of response rate to subsequent next line therapy will be determined in a similar manner as to the primary objective when feasible, where ORR is defined as number (%) of patients with at least one visit response of PR or CR. In instances where data for this post-hoc analysis cannot be obtained and only clinical responses can be obtained (ie patient followed up at an outside institution and only clinical radiograph reports are available), these will be used. Best objective response prior to disease progression will be used. Response rates will be calculated using proportions and the 80% and 95% confidence intervals will be estimated using the exact binomial distribution. Duration of response to next line therapy will be defined as date from next line therapy until date of last dose of next line therapy. The Kaplan-Meier method will be used to assess duration of response to next line therapy.

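### Week-8 changes in T cell markers are used to predict outcomes that, for some patients, are already settled at or before that visit, with no landmark or time-dependent handling

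*Combined protocol and SAP*

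**What the plan says.** Section 10.3 (Data Analyses Plans) lists baseline PD-L1 expression, TILs and on-treatment T cell changes together. Of the last it says that "changes in T cell subpopulations will be used as a continuous variable to predict clinical benefit or overall response rates". It continues: "Cox proportional hazards regression will be used to compare how these biomarkers are associated with PFS and OS as well". PFS and OS both run from treatment initiation. No landmark, delayed entry or time-dependent covariate is mentioned. A separate paragraph adds that changes from baseline will also be examined as pharmacodynamic effects.

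Section 2.3.1 includes "changes in tissue and peripheral T cell receptor genotype" among the markers to be tested as predictors of response. For T cell receptor sequencing, Section 10.3 says: "Descriptive statistics will be used to assess differences from baseline to two months, and their relationship with clinical endpoints".

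On timing, Section 9.2 says: "Research blood samples will be collected at baseline and 2 months, and at end of study or time of discontinuation". Section 9.1 says: "A fresh tissue biopsy of the primary tumor or a metastatic site at baseline and after 2 cycles of treatment will be collected"; with 4-week cycles this is also about W8. In the Section 5.0 schedule, research blood, tumor biopsy and the first on-study CT all fall in the W8 column, and "Scans are to be completed every 8 weeks, regardless of drug holds or treatment delays".

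**The concern.** A change from baseline does not exist until the second sample is drawn. A model that starts the clock at day 1 but uses a value obtained at W8 credits that value with explaining events that had already happened or were found at the same visit. If tumour status at W8 drives the T cell change, and not the reverse, such a model will still show an association with PFS and with response.

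Two groups are affected. For patients with progression or a first response on the W8 scan, covariate and outcome arise together. Patients who progress clinically or die before W8 have no W8 change score, or only a discontinuation sample taken around or after the event. Section 4.9 keeps early clinical progressors in the ORR, PFS and OS assessment, so they either drop out of the marker model silently or enter it with a value that follows the outcome.

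What is at stake is how the result is read: a change produced by response or progression could be reported as a predictive biomarker.

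**Working it through.** **Plan's own figures.** The plan gives no sample size, event count or power for the biomarker analysis. The interim table in Section 1.7.3 does reproduce: ORR 3/18 = 16.7%; clinical benefit (3 + 4)/18 = 38.9% overall, (3 + 2)/7 = 71.4% TNBC, (0 + 2)/11 = 18.2% ER-positive.

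**Step 1. Date of the change score.** Section 10.3 gives no date for the T cell subpopulation change. Blood is scheduled at baseline, 2 months and end of study or discontinuation; tissue at baseline and after 2 cycles (2 × 4 weeks = 8 weeks). W8 is thus the only scheduled on-treatment point, and the T cell receptor paragraph names two months outright. Scans keep to the calendar while the biopsy is tied to cycles, so after a dose delay the biopsy may even follow the W8 scan.

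**Step 2. Patients whose progression is known by W8.** The table's categories are PR, SD of at least 2 months, and PD. With a first scan at W8, PD as best response implies progression at or before that scan. Exact 95% intervals:

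- Pooled: 11/18 = 61% (36% to 83%)
- ER-positive: 9/11 = 82% (48% to 98%)
- TNBC: 2/7 = 29% (4% to 71%), one of the two being pseudoprogression

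Responses first seen at W8 add to these, but the dates of the three PRs are not given. Response status is settled by W8 in 11/18 (61%) if none was first seen then, and in (11 + 3)/18 = 14/18 (78%) if all were. For TNBC the range is 2/7 to 5/7. Leaving out the pseudoprogression patient lowers each count by one.

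**Step 3. Effect on the Cox model.** A simulation (1,500 trials per setting) used a marker change that reflects only W8 tumour status and carries no information about later progression. Assumptions: the W8 progression share is taken from the table; patients free of progression at W8 progress at W16, W24 and so on with probability 0.3 per scan; censoring is at 52 weeks; marker SD is 1. 'Difference' is the marker shift between W8-progressed and other patients. Entries are the percentage of trials with p < 0.05.

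| n, W8 progression share | Difference | Cox from treatment start (median HR) | W8 landmark Cox (median HR) |
|---|---|---|---|
| 28, 61% | 0 | 3.8% (1.00) | 2.9% (1.01) |
| 28, 61% | 0.5 SD | 14.7% (0.82) | 3.8% (1.00) |
| 28, 61% | 1 SD | 46.9% (0.70) | 4.2% (0.99) |
| 20, 29% | 0 | 4.3% (1.00) | 3.6% (1.01) |
| 20, 29% | 0.5 SD | 9.1% (0.86) | 4.5% (1.00) |
| 20, 29% | 1 SD | 22.3% (0.74) | 4.9% (0.99) |

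The marker says nothing about progression after W8, yet the model timed from treatment start often suggests that it does. The landmark model stays at or below about 5%.

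**Step 4. Patients left after a landmark.** For PFS: 18 − 11 = 7 of 18 pooled, 7 − 2 = 5 of 7 TNBC. Scaled to planned sizes: 28 × 7/18 = 10.9, about 11; 20 × 5/7 = 14.3, about 14. For later response, remove any PR already documented by W8 (0 to 3) and keep the pseudoprogression patient: 7 − 3 + 1 = 5 to 7 − 0 + 1 = 8 of 18 pooled, and 5 − 3 + 1 = 3 to 5 − 0 + 1 = 6 of 7 TNBC.

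**The case against.** The strongest reply is that much of the outcome is still open at W8. ORR counts a response at any visit before progression, Section 1.7.2 expects delayed responses, and Section 6.2 lets a response after pseudoprogression count. Clinical benefit through stable disease needs at least 12 weeks. OS is not fixed at W8. All of this stands.

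A reader might infer that response and PFS are largely determined at W8 for most patients, so that the change markers cannot be predictive at all. The documents do not support that. The 11/18 is pooled and driven by ER-positive patients, its interval reaches down to 36%, and in TNBC, the only population of the expansion cohort, the figure is 2/7.

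It is also fair that the Cox sentence speaks of association and not prediction, that T cell receptor changes get only descriptive statistics in Section 10.3, and that T cell subpopulations no longer appear in the exploratory lists of Sections 2.3.1, 6.4 and 10.1, so that marker's status is unclear. But the sentence on response and benefit is explicitly predictive, Section 2.3.1 uses the same language for receptor changes, and the pharmacodynamic analysis is additional and does not replace it.

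Finally, a landmark leaves few patients, and a time-dependent covariate or plain descriptive labelling can be defended equally well. That argues for flexibility over the method, not for leaving the timing unaddressed.

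**Conclusion.** The point holds in a limited form. As written, Section 10.3 uses a post-baseline covariate for events that occur at or before its measurement. The association is concurrent for patients with progression or a first response at W8, undefined for those who progress or die before W8, and prospective for the rest; the plan merges these groups.

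The conclusion rests on the inference that the subpopulation change is measured at about W8, and on reading PD as best response in the interim table as progression by the first scan. The rates of 9% to 47% in the simulation depend on marker differences of 0.5 to 1 SD and a later-progression pattern that are assumed, not documented; the direction follows from the design.

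PD-L1 (stated as baseline) and TILs (read as baseline) are not affected. The analysis is exploratory, with no decision attached, so this is a low-cost improvement and does not threaten the main result.

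**What to change.** Amend Section 10.3 for change-type markers only:

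- State the sampling date of each change score, and whether T cell subpopulations are still planned.
- Analyse PFS from a W8 landmark among patients still progression-free after the W8 scan, and OS from W8 among all patients alive then. Alternatively, enter the change as a time-dependent covariate that takes effect only after the sampling date.
- For later response, include patients with no documented response by W8. Keep those who continue treatment with suspected pseudoprogression under Section 4.1.1, since Section 6.2 allows their later response to count.
- Report W8 change against W8 tumour status as concurrent or pharmacodynamic, not predictive.
- Report the number remaining in each analysis. Leave baseline markers as they are.

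This needs analysis-plan wording only, with no new samples or visits. The cost is smaller sets: for PFS, about 7 of 18 pooled or 5 of 7 TNBC on interim figures. The later-response set depends on PR dates that the documents do not give. Projections to 28 and 20 patients assume planned enrolment; the Amendment 12 entry records closure for low accrual, so the achieved numbers may be lower and descriptive reporting may be all that is feasible.
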